11.2.3 EFFICACY ANALYSES

The analysis of all efficacy endpoints will be based on the Response Evaluable Population.

Efficacy endpoints will be evaluated using RECIST v1.1 criteria, or for subjects with NHL, the revised IWG criteria ([Cheson 2007](#)), or for subjects with mCRPC, a composite response rate defined as any one of the following ([Scher 2016](#)):

- Best response based on RECIST v1.1
- PSA decrease of $\geq 50\%$

- CTC count conversion

Absolute values for PSA and CTCs will be recorded at baseline and response will be analyzed based on percentage of change.

Descriptive analyses of the distribution of ORR, DCR, DOR, TTR, TTP, PFS per RECIST v1.1, the revised IWG criteria, or a composite of any one of the following:

A) Response based on RECIST v1.1; B) PSA decrease of $\geq 50\%$; or C) CTC count conversion, as applicable, and OS will be prepared.

The ORR will be summarized using binomial proportions and confidence intervals computed by the method of Wilson. The examples below display the CI estimates for response within each indication-specific group of approximately 20 enrolled to an expansion cohort. i.e. at the 95% CI, 0 of 20 responses observed excludes an ORR of 16%.

Numerator	Denominator	Proportion	Lower	Upper
0	20	0	0	0.161
1	20	0.05	0.009	0.236
2	20	0.10	0.028	0.301
3	20	0.15	0.052	0.360
4	20	0.20	0.081	0.416
5	20	0.25	0.112	0.469
6	20	0.30	0.145	0.519
7	20	0.35	0.181	0.567
8	20	0.40	0.219	0.613
9	20	0.45	0.258	0.658
10	20	0.50	0.299	0.701
11	20	0.55	0.342	0.742
12	20	0.60	0.387	0.781
13	20	0.65	0.433	0.819
14	20	0.70	0.481	0.855
15	20	0.75	0.531	0.888
16	20	0.80	0.584	0.919
17	20	0.85	0.640	0.948
18	20	0.90	0.699	0.972
19	20	0.95	0.764	0.991
20	20	1	0.839	1

The distribution of DOR, in the subset of subjects responding will be summarized using Tukey's five number summary, including the minimum, mean, median, maximum and

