## 9.2. General Data Handling Conventions

#### 9.2.1. Data Displays for Reporting

For tables and figures the data will be displayed as shown in the following tables. Any abbreviation used in the column text will be displayed in full description text in the footnote of the output.

Unless specified otherwise all tables will have corresponding listings supporting the table summaries. The default ordering of the listings is by disease categories, site ID, subject ID, test or parameter name (if applicable), sequence number (AE, medical history, or medication), date of event or date of collection (if applicable).

For study population and efficacy, the columns will be grouped by the primary tumor type regardless if a subject was enrolled under escalation or expansion stage.

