**Table 1: Data Display for Study Population and Efficacy**

Column Text Display	Description Verbatim terms included in the grouping (including misspelling and specific terms present in the clinical data)	Display Order
CRC	Metastatic Colorectal Cancer Metastatic colorectal Metastatic Colorectal Carcinoma With Abdomial* Mass Colorectal Adenocarcinoma	1
HGSOC	High Grade Serous Ovarian Cancer Platinum resistant ovarian Carcinosarcoma Of Ovary – CCNE1 Amplification: No High grade serous ovarian cancer Platinum-Resistant High Grade Papillary Serous Carcinoma Of The Ovary Serous Adenocarcinoma Peritoneum/Ovary	2
NSCLC	Advanced Non-small cell Lung Cancer Advanced non small cell lung	3
mCRPC	Metastatic Castration-Resistant Prostate Cancer Metastatic castration resistant* prostate Prostate Adenocarcinoma Adenocarcinoma of Prostate	4
HNSCC/SCCA	Head and Neck Squamous Cell Carcinoma Head and neck squamous cell	5
	Squamous cell carcinoma of the anus	
Other	Disease types not included in the previous columns	6
Overall	All subjects in the population	7

\* Misspelling are present in the clinical database and will be kept verbatim for programming purposes

For safety summaries, the columns will be group based on Cycle 1 Day 1 total dose level. For subjects without Day 1 treatment they will be included in the “<=800mg” column.

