## 9.2.2. Reporting Conventions

The general programming considerations for tables, listings, and figures (TLFs) are provided in [Section 15](#). Actual formats and layouts may be altered slightly to accommodate actual data or statistics. Minor format changes will not require updates to the SAP. The TLF numbering and general content follow the ICH E3 guidelines.

In general, continuous variables will be summarized to include the population sample size (N), number of subjects with available data (n), arithmetic mean, standard deviation, median, minimum, Q1, Q3 and maximum values. Categorical variables will be summarized by the population size (N), number of subjects in each category, and the percentage of subjects in each category. A missing category will be added as the last category if appropriate.

The data analyses will be conducted using the SAS® System (SAS Institute Inc., Cary, NC) version 9.4 or above. The eClinical Solutions' standard operating procedures will be followed for the validation of all SAS programs and outputs.

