### **9.3. Data Definition and Deviations**

#### **9.3.1. Baseline and Change from Baseline**

In general, the last recorded value prior to the first study treatment will serve as the baseline measurement for the safety endpoints such as lab, vital signs, and electrocardiograms (ECGs). The first treatment could be the first dose for PK collection or, if PK dose is not implemented, the first dose during the treatment phase. If there are multiple results collected on the same day, the collection done at later time, with the repeat status, or with a later sequence number will be used.

Change from baseline will be calculated as the post baseline value minus the baseline value. Percentage change from baseline will be calculated as the change from baseline divided by the

baseline value, multiplied by 100. If either the baseline or post-baseline value is missing, then change from baseline and percentage change from baseline will be set to missing.

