**Table 5: Analysis Visit Windowing Rules for Tumor Markers**

Analysis Visit Name	Target Study Day	Visit Windowing
Baseline	NA	Last assessment prior to first dose
End of Cycle 1	28	21 to 35
End of Cycle 2	56	49 to 63

Analysis Visit Name	Target Study Day	Visit Windowing
End of Cycle n	28 * n	(28 * n - 7) to (28 * n + 7)

Once the analysis visit windowing rules are applied, the result closest to the target study day will be used for summary purpose. If multiple results have the same distance to the target study day the later one will be used. If both results fall on the same day, the one with the larger sequence number will be used.

CEA, PSA, and CA-125 will be summarized descriptively by actual value at each analysis visit and change from baseline at each post-baseline visit. All other tumor markers will be listed only.

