14.3.3.4	Shift Table of L/N/H Classification for Biochemistry Laboratory Parameters from Baseline	Safety
14.3.3.5	Tumor Marker Parameters	Safety
Other Safety		
14.3.4	Vital Sign Parameters	Safety
14.3.5	Local Electrocardiograms Parameters	Safety
Note: PK and QTc reports will be provided in the clinical study report. Separate analysis of these endpoints will not be done.		

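### The SAP omits, without declaring it, the protocol's percentage-change analysis of PSA in mCRPC; its only marker table shows absolute change by starting dose

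*SAP*

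**What the plan says.** **Protocol 11.2.3** defines response in mCRPC as a composite: RECIST response, a PSA decrease of at least 50%, or CTC conversion. For PSA and CTCs it adds that "response will be analyzed based on percentage of change".

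**SAP 11.1.6** says mCRPC response will also be judged by PSA and CTC, but sends the data to listings (16.2.2.8 and 16.2.2.9). It derives no PSA response and plans no summary.

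**SAP 12.4**, below Table 5: "CEA, PSA, and CA-125 will be summarized descriptively by actual value at each analysis visit and change from baseline at each post-baseline visit".

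**SAP 9.3.1** fixes the scale: "Change from baseline will be calculated as the post baseline value minus the baseline value". It defines the relative measure separately: "Percentage change from baseline will be calculated as the change from baseline divided by the" baseline value, times 100. Section 12.4 asks only for the first.

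**SAP 16.1** has one marker table, 14.3.3.5, "Tumor Marker Parameters", on the Safety population. **SAP 9.2.1** sets its columns: "For safety summaries, the columns will be group based on Cycle 1 Day 1 total dose level". Tumor-type columns are kept for other displays: "For study population and efficacy, the columns will be grouped by the primary tumor type".

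**SAP 9.2.2** sets the statistics for continuous variables, which include "arithmetic mean, standard deviation, median, minimum, Q1, Q3 and maximum values".

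**SAP 13** lists five changes from the protocol: disease-type groupings, exploratory biomarkers not collected, the exposure-QTc endpoint, the interim reviews, and the alternative response population. PSA analysis is not among them.

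**The concern.** Preliminary efficacy in the indication-specific cohorts is a primary objective (Protocol 3.1.1), and mCRPC is one of the six cohorts. PSA decrease is one of three routes to response there. If the SAP is followed as written, the tables will contain no PSA percentage change and no PSA response rate. Nor will Section 13 tell a reader that a protocol analysis was dropped.

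The gap is wider for some subjects. Protocol 4.2.1, criterion 8, admits mCRPC subjects on rising PSA or a CTC count alone. SAP 8.2 requires measurable disease at baseline under both definitions of the Response Evaluable Population, and every efficacy table in SAP 16.1 uses that population.

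**Working it through.** The plan states no figure for this summary, so the first steps set the texts side by side. The arithmetic then shows what the planned table can and cannot tell the reader.

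**1. Tracing the protocol requirement**

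| Protocol 11.2.3 asks for | Where the SAP could supply it | What is there |
|---|---|---|
| PSA on percentage change | 12.4, Table 14.3.3.5 | Actual value and absolute change |
| PSA decrease of at least 50% as a response | 11.1.6; efficacy tables in 16.1 | Listings only |
| Any departure declared | 13 | Not mentioned |

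**2. Who is covered.** An mCRPC subject who enters on PSA or CTC without measurable disease fails condition 1 of SAP 8.2. He is therefore in no efficacy table. Listing 16.2.2.8 (PSA) is also assigned to the Response population. He is in the Safety population, so Table 14.3.3.5 is the only planned summary containing his PSA.

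**3. What the table would show.** The documents give no PSA distribution, so all values here are assumed. Nine subjects fall from 20 to 8 and one rises from 2000 to 3000.

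- Mean absolute change: (9 × (8 − 20) + (3000 − 2000)) / 10 = (−108 + 1000) / 10 = +89.2.
- Median, Q1 and Q3 of absolute change: all −12.
- Percentage change: (8 − 20)/20 = −60% in nine, (3000 − 2000)/2000 = +50% in one; median −60%.
- Decrease of at least 50%: 9/10. Wilson interval with z = 1.96: centre (p + z²/2n)/(1 + z²/n) = (0.9 + 0.192)/1.384 = 0.789; half-width z·√(p(1−p)/n + z²/4n²)/(1 + z²/n) = 1.96 × √(0.0090 + 0.0096)/1.384 = 0.193; interval 0.596 to 0.982.

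The same formula reproduces the protocol's own Wilson table: 0/20 gives 0 to 0.161, 4/20 gives 0.081 to 0.416, and 10/20 gives 0.299 to 0.701.

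**4. How far extreme values matter.** A simulation used log-normal baselines (median 50, log-SD 1.0 to 2.0), a ratio to baseline with median 0.8 and log-SD 0.6, n = 10 or 20, and 20,000 samples per setting, all assumed.

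| Quantity | Range over settings |
|---|---|
| Two largest changes, share of summed absolute change (median) | 41% to 77% |
| Mean absolute change opposite in sign to median percentage change | 27% to 33% of samples |
| Median absolute change opposite in sign to median percentage change | 2% to 6% of samples |

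The mean and SD are fragile. The median is not.

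**5. Why the median is still not enough.** A change of −10 is −10/20 = −50% from a baseline of 20, and −10/2000 = −0.5% from a baseline of 2000. The table summarizes values and changes as separate distributions, so a subject's change is not tied to his own baseline. The number reaching the 50% threshold cannot in general be recovered from it.

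**The case against.** Four counter-arguments deserve weight, and each rules out a stronger reading that a reader might infer.

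- **A few very high values decide the table.** Not supported. SAP 9.2.2 requires median and quartiles beside the mean and SD. In the example above the reader would see −12 for all three, with the outlier visible in the maximum.
- **The table pools all tumor types.** This is true of the column layout, but the markers are summarized one by one and Protocol 7.2.1 ties collection to disease. PSA rows should be mostly prostate and CA-125 rows mostly ovarian. No text restricts a marker's rows to its tumor type, so mixing is plausible mainly for CEA; the documents do not show its extent.
- **Table 14.3.3.5 itself contradicts the protocol.** Not supported. It is a safety-section summary that could stand beside a response analysis. The defect is that 12.4 does not supply the percentage change, 11.1.6 stops at listings, and 13 is silent.
- **CEA and CA-125 raise the same conflict.** They do not. The protocol's sentence names only PSA and CTCs, neither CEA nor CA-125 is a listed efficacy endpoint, and Appendix 2 says markers alone cannot establish objective response.

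It is also fair to say that individual values remain available in the PSA listing and in Listing 16.2.3.6. The measurable-disease requirement is inherited from Protocol 11.1.2, not introduced by the SAP. Neither argument supplies the missing summary for mCRPC subjects who do have measurable disease, and neither replaces a declaration in Section 13.

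**Conclusion.** The point holds for PSA in mCRPC. The protocol specifies a percentage-change analysis with a 50% threshold, no SAP table provides it, and Section 13 does not say so. For mCRPC subjects without measurable disease, the only planned PSA summary is on an absolute scale by starting dose.

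The size is minor. All these outputs are descriptive, no error rate or decision rule depends on them, and the raw values are collected. What is lost is a protocol-specified quantity that no statistic of absolute change can show. The textual finding needs no assumption. Every PSA value in the example and simulation is assumed, and the documents do not say how many mCRPC subjects will lack measurable disease. The layout for CEA and CA-125 is a matter of presentation only.

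**What to change.** In SAP 11.1.6 and 12.4, add one efficacy table for all mCRPC subjects with a baseline PSA, whether or not they have measurable disease. It should give:

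- percentage change by analysis visit (median, quartiles), using the definition already in 9.3.1;
- best percentage change (median, quartiles), taken over all post-baseline values whether or not they fall in a Table 5 window;
- the number and proportion with a decrease of at least 50%, with Wilson 95% CI, stating which post-baseline values count.

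Add the table to 16.1. If the sponsor prefers not to produce it, add a bullet to Section 13 that declares and justifies the omission.

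As an optional improvement, show Table 14.3.3.5 in the tumor-type columns of SAP Table 1 (CA-125 in HGSOC, CEA in CRC) and include percentage change.

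The cost is one added table, short text edits and, if wanted, a column change in one planned table. No new data are needed.

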## 12.5. Vital Signs

Vital sign data including blood pressure, pulse rate, and body temperature are collected before the first dose for PK, Day 1, 8, 15, and 22 of Cycle 1, Day 1 of the subsequent cycles, and at the safety follow-up.

For all parameters, actual values and change from baseline will be presented for scheduled visits using descriptive statistics for continuous variables.

## 12.6. ECG

Both central and local ECG data are collected in this study. Local ECGs are collected at screening, Cycle 1 Day 1, Cycle 2 Day 1, every third cycle Day 1, and at the safety follow-up. Central ECGs are collected at pre-dose and 2 hours after the first PK dose and at pre-dose, 1, 2, 4, 6, and 24 hours after the Cycle 1 Day 22 dose.

Both local and central ECGs include ventricular rate, QRS rate, QT interval, QTcF interval, PR interval, RR interval, and interpretation. Local ECG parameters will be presented using the actual values and change from baseline for each of the scheduled visits using descriptive statistics for continuous variables. If triplicates are collected for ECG parameters, the average value of the triplicates and the last interpretation will be used for reporting purpose.

The Central ECGs will be analyzed with the PK data to explore the exposure-QTc relationship in a separate report and will not be covered in this SAP.

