3.1.3 EXPLORATORY OBJECTIVES AND ENDPOINTS

Exploratory objectives	Endpoints
To investigate the pharmacodynamics of SRA737 in tumor tissue	Proof of target engagement and changes in mechanism of action biomarkers between baseline and on treatment with SRA737, including, but not limited to: pSer296 Chk1, pS317 Chk1 and total Chk1
To investigate the pharmacodynamics of SRA737 in surrogate tissues such as blood or peripheral blood mononuclear cell (PBMCs)	Proof of target engagement and changes in mechanism of action biomarkers between baseline and on treatment with SRA737, including but not limited to: pS317 Chk1, pS345 Chk1, total Chk1, gammaH2AX and RAD51
To explore possible clinical predictors of outcomes	Characteristics such as performance status, prior therapy, indication and other known or potential prognostic or predictive factors
To explore the relationship between exposure (PK) and QT/QTc, other electrocardiogram (ECG) parameters and cardiovascular safety findings	Association of QT, QTc, blood pressure (BP), heart rate, other ECG intervals with time-matched PK concentrations. Profile of QTc over the dosing interval

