11.2.4 PK/QTC

Time-matched ECG measurements and PK samples will be collected after a single dose of SRA737 on Day -7 to Day -4 and during Cycle 1 (See Section 7.7 for the Schedule of Secondary and Exploratory Assessments).

A concentration-effect model will evaluate the relationship between plasma concentrations and the mean change from Baseline in QTcF for all subjects in the PK/QTC study.

Plasma concentrations of SRA737 will be determined using a validated bioanalytical method and summarized using descriptive statistics. Pharmacokinetic parameters, including but not limited to C_{min} , C_{max} , T_{max} , AUC, $t_{1/2}$, total body clearance, and apparent volume of distribution, will be determined using non-compartmental method(s). PK data generated from this study

may be used in conjunction with PK data from other clinical studies in future meta-analyses for population PK assessment. These data will be reported separately.

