#### **9.2.4. Analysis Visiting Windows**

No analysis visit window will be defined for safety data or efficacy data except for the tumor marker data. All post-baseline radiological disease assessments will be used for analyses purpose. Nominal clinical visits that are defined in the protocol “Schedule of Event” will be used for summary of safety endpoints. Any unscheduled safety data will not be included in the by-visit summary and will be included in the listings.

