### 12.3. Laboratory Evaluations

Biochemistry and hematology laboratory tests are scheduled to be collected before the first dose for PK, at Day 1, 8, 15, and 22 for each cycle (frequency could be reduced at later cycles), and at the safety follow-up (30 days after the last dose). Troponin T or I are collected before the first dose for PK, Day 1 and Day 8 of Cycle 1 and Day 1 of Cycle 2 and Cycle 6, and at the safety follow-up. Urinalysis is collected before the first dose for PK, Day 1 of each cycle, and at the safety follow-up.

All continuous laboratory parameters in biochemistry and hematology will be summarized descriptively by actual value at each scheduled visit and the corresponding changes from baseline. The maximum post-baseline and minimum post-baseline (including both scheduled and unscheduled results) will also be provided before the by-visit summary. All parameters will be summarized in SI units.

Shift tables from baseline to visit will be provided for hematology and chemistry parameters to display low, normal, high, and missing values by treatment group in a 3-by-3 contingency table. Denominators for percentages will be the number of subjects with non-missing data at the specific assessment and baseline.

Urinalysis results will only be provided in the listing.

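### No output specified in the SAP gives each subject's worst on-treatment local QTcF or counts subjects above a QTcF cut-off, and unscheduled ECGs reach only a listing

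*SAP*

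**What the plan says.** SAP 12.6 lists QTcF among the local ECG parameters and sets the display: "Local ECG parameters will be presented using the actual values and change from baseline for each of the scheduled visits". SAP 9.2.2 defines the continuous summary as N, n and "arithmetic mean, standard deviation, median, minimum, Q1, Q3 and maximum values". For ECGs taken outside the schedule, SAP 9.2.4 says: "Any unscheduled safety data will not be included in the by-visit summary and will be included in the listings".

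The output lists agree. SAP Table 6 has one ECG table (14.3.5, local parameters), Table 7 has no ECG figure, and Table 8 has one ECG listing (16.2.3.8).

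Laboratory data are treated differently. SAP 12.3 adds to its by-visit summary: "The maximum post-baseline and minimum post-baseline (including both scheduled and unscheduled results) will also be provided". It also has shift tables. Vital signs follow the ECG layout: "actual values and change from baseline will be presented for scheduled visits using descriptive statistics for continuous variables" (SAP 12.5).

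Central ECGs are handled elsewhere: "The Central ECGs will be analyzed with the PK data to explore the exposure-QTc relationship in a separate report" (SAP 12.6). SAP section 4 sends secondary and exploratory endpoints to separate reports, and SAP 13 promises a QTc report within the clinical study report.

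**The concern.** Two questions about QTcF safety are how high each subject went and how many subjects went above a given level. A by-visit table answers neither. Its maximum is the highest value across subjects at one visit. It shows whether anyone crossed a cut-off there, but not how many did, and it does not combine a subject's values over visits. It also leaves out the unscheduled ECG. Protocol 7.2.2 schedules the on-treatment local ECGs predose, so an unscheduled tracing taken for a suspected problem may be the informative one.

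The trial is first-in-human, and Protocol 5.5.1.4 says QT potential had not been assessed clinically while allowing QT-prolonging drugs with caution. Protocol 7.2.2 and 7.7 also let the sponsor stop central ECGs once the exposure-QTc data suffice. For any subject enrolled after that, local ECGs would be the only QTcF data. Nothing in the documents shows that this happened.

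**Working it through.** **1. Outputs specified in the SAP (Tables 6 to 8).**
- ECG tables: 1, by scheduled visit.
- ECG figures: 0.
- ECG listings: 1.
- Outputs deriving a worst post-baseline QTcF per subject: 0.
- Outputs counting subjects above a QTcF or change-in-QTcF cut-off: 0.

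The plan states no figure on this point, so there is none to reproduce.

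**2. Do the by-visit statistics determine the count?** Take one visit and one column, with change in QTcF (ms) for 50 subjects. Sets A and B share their lowest 38 values:

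-28, -23, -20, -18, -16, -15, -14, -12, -11, -11, -10, -9, -8, -7, -7, -6, -5, -5, -4, -3, -3, -2, -2, -1, 0, 0, 1, 2, 2, 3, 3, 4, 5, 5, 6, 7, 7, 8.

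- Top 12 of A: 8, 8, 8, 9, 11, 33, 43, 44, 44, 45, 45, 65.
- Top 12 of B: 10, 14, 15, 16, 21, 21, 25, 26, 27, 61, 62, 65.

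Each top 12 sums to 363, with sum of squares 15,479. The shared 38 sum to -187, with sum of squares 3,863. In both sets:
- mean = (363 - 187)/50 = 176/50 = 3.52
- SD = sqrt[(15,479 + 3,863 - 50 × 3.52²)/49] = 19.55
- minimum -28, Q1 -8, median 0, Q3 8, maximum 65

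| | A | B |
|---|---|---|
| Above 60 ms | 1/50 (2%) | 3/50 (6%) |
| Above 30 ms | 7/50 (14%) | 3/50 (6%) |

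The printed change statistics are identical and the counts differ. The example covers change values in one undivided column only. Table 14.3.5 would also show actual values, split into the two dose columns and Overall.

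**3. Scheduled local ECGs for a subject treated for 4 cycles (Protocol 7.2.2, 7.3, 7.7).**
- On repeat dosing: Cycle 2 Day 1, predose, so 1 recording. It is 2 if the every-third-cycle rule is read as including Cycle 3.
- Post-baseline but not on repeat dosing: Cycle 1 Day 1 predose (only if a run-in PK dose was given, at least 4 days earlier) and safety follow-up (30 ± 7 days after the last dose).
- All post-baseline: 2 to 3, or 3 to 4 on the other reading.
- Central schedule, for comparison: 1 post-dose recording after the run-in dose and 5 on Cycle 1 Day 22, so 6.

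A worst value over all post-baseline ECGs would mix one on-drug trough reading with up to two taken well away from dosing. It should be limited to on-treatment ECGs.

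**4. How far worst values read high by chance.** Assume no drug effect, normal changes with SD 10 to 15 ms (not a figure from the documents), and m independent recordings. Then P(worst change > c) = 1 - Φ(c/SD)^m.

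| m | >30 ms, SD 10 | >30 ms, SD 15 | >60 ms, SD 15 |
|---|---|---|---|
| 1 | 0.13% | 2.28% | 0.003% |
| 3 | 0.40% | 6.67% | 0.010% |
| 6 | 0.81% | 12.90% | 0.019% |

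By simulation, the mean worst change is 8.5 to 12.7 ms for m = 3 and 12.7 to 19.0 ms for m = 6. If recordings correlate at 0.5 through the shared baseline, exceedance of 30 ms at SD 15 falls to 5.7% (m = 3) and 9.6% (m = 6). A count above 60 ms is almost free of this inflation under these assumptions; a count above 30 ms is not.

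**The case against.** The strongest reply is scope. QT/QTc is an exploratory endpoint, the named primary safety endpoints are adverse events, laboratory tests and vital signs, and SAP section 4 assigns exploratory endpoints to separate reports. That stands, and it limits the weight of the point. It does not remove it, because SAP 12.6 keeps local ECGs within this SAP as safety data.

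A reader might infer that the trial will report no QTcF outlier counts at all, since SAP 13 and the note to Table 6 rule out separate analysis of these endpoints. The documents do not support that. Both places first promise a QTc report, and the natural reading is that no further tables will be made under this SAP. The protocol describes the QTc work as a model ("A concentration-effect model will evaluate the relationship between plasma concentrations and the mean change from Baseline in QTcF") and a profile ("Profile of QTc over the dosing interval"). Neither description promises counts or excludes them.

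Three other points stand in part:
- **Existing visibility.** The by-visit maximum would alert a reader (both example sets print 65 ms), and Listing 16.2.3.8 shows individual results. Counting from it would be by hand. Adverse event tables catch ECG abnormalities only where the investigator judged that they met the definition in Protocol 10.1.1, such as needing intervention or further work-up.
- **Consistency.** Vital signs are treated the same way and echocardiograms are only listed, so the layout is not an oversight peculiar to ECGs.
- **Small gain from scheduled ECGs.** With one scheduled on-treatment ECG, the subject's worst scheduled value is the Cycle 2 Day 1 value already summarised. The gain there is the count of subjects and the inclusion of unscheduled tracings.

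**Conclusion.** The point holds as a modest gap in safety reporting. No output specified in this SAP gives worst on-treatment QTcF per subject or a count above a cut-off, and unscheduled ECGs enter no summary. No primary estimate or dose rule changes, and Protocol 2.3.5.3 judges preclinical cardiac risk minimal.

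The likely size of the gap cannot be stated from the documents. It would be wrong to read the 1-versus-3 and 7-versus-3 counts as an expected error: the sets were built to match, their SD of 19.55 ms exceeds the 10 to 15 ms assumed for the chance calculation, and they show only that change statistics in one column do not fix the count. The chance-exceedance figures rest on the assumed SD, normality and no drug effect. Whether central-ECG counts will appear depends on a QTc report whose content is not specified.

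**What to change.** In SAP 12.6 and Table 14.3.5, add from local ECGs already collected:
- Each subject's worst on-treatment QTcF and worst change from baseline. On-treatment means after Cycle 1 Day 1 dosing and up to a short, fixed window after the last dose. Show Cycle 1 Day 1 predose and the safety follow-up separately.
- Number and percentage of subjects above 450 ms (men) and 470 ms (women), the entry limits in Protocol exclusion criterion 13, and above higher absolute and change cut-offs fixed before the table is run. Possible choices are 480 and 500 ms, and 30 and 60 ms; these are not from the documents.
- Two rows: scheduled ECGs alone, and scheduled plus unscheduled.
- As denominator, subjects with a baseline and at least one on-treatment QTcF.

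One added sentence in SAP 12.6 could state whether the QTc report gives the same counts for central post-dose ECGs.

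The cost is one table section and SAP wording, with no new data collection. Three downsides belong in a footnote:
1. Worst values read high by chance, and more so with more recordings: 2.3%, 6.7% and 12.9% above 30 ms for 1, 3 and 6 independent recordings at SD 15 ms.
2. Unscheduled ECGs may be clinically triggered and accumulate with time on treatment, so that row should not be used to compare the two dose columns.
3. Scheduled on-treatment local ECGs are predose and may miss the peak, so a low count is not evidence of safety.
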